A total of two blood samples will be drawn over the course of the study - once at baseline and once after treatment has been completed. A trained, experienced nurse or phlebotomist will draw the blood. These blood samples will be processed by the VA laboratory to test for inflammatory markers, and the results will be uploaded to the participant's secure medical file. If they consent to storage of blood samples, the samples will later be used to examine genetic material.

If we are unable to complete labwork, overnight PSG or in-person cognitive tests due to VA restrictions or participant refusal as a result of COVID-19 concerns, we will not exclude these participants from the study.

TREATMENT

Our hypotheses will be tested in a randomized parallel groups design. Randomization will be based on type of treatment assignment: either to Cognitive Behavior Therapy for Insomnia (CBT-I) or Arousal-Based Therapy for Insomnia (ABT-I)(previously referred to as Desensitization Therapy for Insomnia) for the 6-week treatment phase.

CBT-I (SR & CT):

The CBT-I adopted in this trial will be based on our large-scale VA implementation of CBT-I and includes a published sleep self-help book, a published therapist guide, and the CBT-I therapist manual appended. It comprises both SR and CT as outlined below. The CBT-I therapy protocol consists of six sessions (an initial assessment and five treatment sessions). Treatment begins with a comprehensive sleep assessment and case conceptualization, which are used to guide selection and sequencing of CBT-I components. Treatment components include stimulus control, sleep restriction therapy, relaxation, and cognitive therapy. The final session focuses on maintenance of gains and relapse prevention.

Sleep Restriction Therapy (SR). The initial Time in Bed (TIB) prescription is calculated on the average total sleep time (TST) reported by subjects in their baseline sleep logs. Subsequently, the TIB prescription is determined using the formula: TIB = average TST. An additional treatment criterion is that prescribed initial time in bed should never be below 5 hours, even if the average total sleep time (TST) is very low (e.g., 3 hours). After one week, depending on subject's daily sleep logs and discussion with participant about tolerability, the therapist suggests a new TIB prescription. The

Title : Non-Pharmacological Treatments for Insomnia in Chronic Traumatic Brain Injury
Approval Period: 07/31/2024 - 07/31/2025

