The Protocol Director will review all Adverse Events and Serious Adverse Events as soon as possible after the occurrence. SAEs are reported and forwarded to IRB as appropriate.

Title : Non-Pharmacological Treatments for Insomnia in Chronic Traumatic Brain Injury
Approval Period: 07/31/2024 - 07/31/2025

5. If applicable, how frequently will the Monitoring Committee meet? Will the Monitoring Committee provide written recommendations about continuing the study to the Sponsor and IRB?

Information about adverse events is collected at each visit by the interviewer. Any potentially serious problem is brought immediately to the Protocol Director. All data entered into the database is monitored by the senior research associate and the database manager.

6. Specify triggers or stopping rules that will dictate when the study will end, or when some action is required. If you specified this in Section 2g [Study Endpoints], earlier in this application enter 'See 2g'.

Criteria for discontinuation of a patient in the study will include an increase in bothersome nightmares for a week under treatment. We have not seen consistent reporting of nightmares with the proposed treatments, however that is always possible, hence again we would want to make sure that that occurred for at least a week before a patient was discontinued. Patients will be allowed to continue in the protocol after an SAE independent of treatment, e.g. hospitalization following a fall. All treatments are considered active and patients will be allowed to continue their treatment as a courtesy. However, data from such subjects will not be included in statistical analyses since such SAEs may affect sleep. Patients will not be restarted if their sleep deteriorates meeting the above criteria and they are discontinued from the protocol.

7. Indicate to whom the data and safety monitoring person, board, or committee will disseminate the outcome of the review(s), e.g., to the IRB, the study sponsor, the investigator, or other officials, as appropriate.

Serious Adverse Events are reported to the IRB using the standard reporting forms.

8. Select One:

The Protocol Director will be the only monitoring entity for this study.
 This protocol will utilize a board, committee, or safety monitor as identified in question #2 above.

10. Benefits

a) **Describe the potential benefit(s) to be gained by the participants or by the acquisition of important knowledge which may benefit future participants, etc.**

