16. Attachments

Attachment Name	Attached Date	Attached By	Submitted Date
TBI-CBTi final submission	07/28/2017	[name]	
VARQs [name] 41040	07/28/2017	[name]	
VA Business Card	10/15/2018	[name]	
Directions & Contact	10/15/2018	[name]	
Q&A	10/15/2018	[name]	
Acute_Unstable_Chronic_Illness_Checklist	10/25/2018	[name]	
BerlinSleepApnea	10/25/2018	[name]	
Boston_Lifetime_Assessment_TBI_Questionnaire	10/25/2018	[name]	
Boston_Lifetime_Assessment_TBI	10/25/2018	[name]	
Brief_Pain_Inventory	10/25/2018	[name]	
Credibility_Expectancy_Questionnaire	10/25/2018	[name]	
Epworth_Sleepiness_Scale	10/25/2018	[name]	
Functional Outcomes of Sleep Questionnaire	10/25/2018	[name]	
Insomnia_Severity_Index	10/25/2018	[name]	
MedicationList	10/25/2018	[name]	

Title : Non-Pharmacological Treatments for Insomnia in Chronic Traumatic Brain Injury
Approval Period: 07/31/2024 - 07/31/2025

MINI 7.0.2 Standard	10/25/2018	[name]	
Penn_State_Worry_Questionnaire	10/25/2018	[name]	
PTSD_Checklist_DSM5	10/25/2018	[name]	
Sleep Diary - Consensus E	10/25/2018	[name]	
Treatment_Satisfaction	10/25/2018	[name]	
Veteran's Rand 36 Item Health Survey	10/25/2018	[name]	
Working_Alliance_Inventory for Participant	10/25/2018	[name]	
Working_Alliance_Inventory for Therapist	10/25/2018	[name]	
DUKE	10/25/2018	[name]	
CANTAB Cognitive Test Security Info	10/25/2018	[name]	
PSG - Compumedics Siesta Brochure	10/25/2018	[name]	
PSG - Compumedics Quik-Cap Brochure	10/25/2018	[name]	
Morningness Eveningness Questionnaire	10/25/2018	[name]	
CANTAB Cognitive Test Overview	10/25/2018	[name]	
CBTI - A Guide to Overcoming Insomnia	10/25/2018	[name]	
CBTI - Behavioral Experiments record sheet	10/25/2018	[name]	
CBTI - Brief Positive and negative beliefs about sleep-related worry quaire	10/25/2018	[name]	
CBTI - Case Conceptualization Form	10/25/2018	[name]	
CBTI - Cognitive restructuring questions	10/25/2018	[name]	
CBTI - Definition of automatic thoughts	10/25/2018	[name]	
CBTI - Management of unwanted thought handout_vic	10/25/2018	[name]	
CBTI - monitoring examples	10/25/2018	[name]	

Title : Non-Pharmacological Treatments for Insomnia in Chronic Traumatic Brain Injury
Approval Period: 07/31/2024 - 07/31/2025

handout			
CBTI - Monitoring for information about sleep	10/25/2018	[name]	
CBTI - Monitoring for monitoring form	10/25/2018	[name]	
CBTI - Personalized case conceptualization	10/25/2018	[name]	
CBTI - Questions and Answers about Guidelines	10/25/2018	[name]	
CBTI - Reasons for Feeling Tired	10/25/2018	[name]	

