APPROVAL LETTER/NOTICE NOTE: List all items (verbatim) that you want to be included in your approval letter (e.g., Amendment date, Investigator's Brochure version, consent form(s) version(s), advertisement name, etc.) in the box below.

By checking this box, I verify that I, as the Protocol Director (PD) responsible for this research protocol, have read and agree to abide by the above obligations, or that I have been delegated authority by the PD to certify that the PD has read and agrees to abide by the above obligations.

Statistical Analysis Plan

In testing Hypotheses 1 and 2, treatment response will be evaluated in terms of improvement in the Insomnia Severity Index (ISI) from baseline to end of the 6-week treatment.

Primary Hypothesis 1: Efficacy of CBT-I compared to a manualized active control condition, Arousal Based Therapy for Insomnia (ABT-I). To test the hypothesis that CBT-I will show efficacy for insomnia in TBI patients at the end of the 6-week treatment period, compared to the control condition (ABT-I) we will regress change in ISI on treatment (CBT-I versus ABT-I; 6 weeks vs. baseline). We will run analogous models to test for persistent treatment effects at the 16 and 24-week follow-up points. In each set of models the dependent variable will first be the change relative to baseline in our primary outcome measure of insomnia change defined by the ISI scores. We will covary for comorbid PTSD severity and amount of medication use (SSRIs) as required, if the frequency of such differs by treatment group.

Secondary Hypothesis 2: Moderators and Mediators of response. Our previous design separated Sleep Restriction (SR) and Cognitive Therapy (CT) components of CBT-I, however, we feel that although the design of the study has been changed, we can still gather some preliminary data on likely moderators and mediators of CBT-I, SR and CT while conducting the clinical trial and testing our Primary Hypothesis. Thus, we can still determine whether changes in potential moderators and mediators of SR and CT might also moderate or mediate the effects of the entire CBT-I package.

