Exploratory analyses will compare the predictive usefulness of all measures listed in Table 5. In more detail, we will fit regression models for change in ISI on treatment, the continuous moderator and the treatment by moderator interaction. Baseline Medication use and PTSD should be similar across groups due to randomization and use of the blocking procedures (Section 2.a.3.b.5). The analysis may be adjusted for other covariates (age and alcohol use) if they are significantly different between groups at baseline despite randomization. We will use percentile, bootstrap confidence intervals to determine the moderator value, if any, at which there is a change in the optimal choice of treatment (i.e. the point of intersection at which one treatment first surpasses another). Our results will allow us to choose the optimal treatment based on individual moderator values and estimate the comparative advantage of one treatment over another given a specific moderator value. The confidence intervals will also show the moderator values, if any, for which the difference between treatments is statistically or clinically insignificant.

Secondary Hypothesis 2: Mechanisms of Action (Mediators). As in the case of moderators of treatment response, since our design has changed mediators of treatment response are reduced in prominence in this proposal. Nonetheless, we feel some exploratory analyses may be carried out. For example, we hypothesize that changes in TIB with its associated increase in homeostatic pressure for sleep may account for some of the effects of SR and that changes in measures of worry and pain may explain some of the effects of CT. In the package of combined SR plus CT (CBT-I) this may still be the case for the group as a whole. Therefore, we will conduct secondary analyses using the bootstrap strategy for mediator analysis formulated by Preacher and Hayes [98] to address this possibility. Specifically, we will fit three separate regression models to estimate the indirect effect of treatment through the mediator: 1) Change in ISI on treatment; 2) Change in mediator on treatment; and 3) Change in ISI on treatment plus change in mediator. Each model will be adjusted for the same covariates described above. We will estimate the indirect effect as the product of the treatment effect in (2) and the mediator

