effect in (3). We will compare the indirect effect to the total effect of treatment, estimated in (1), to determine how much of the total effect of treatment is accounted for by the mediator. Due to the non-normality of the estimates, percentile bootstrap confidence intervals for the mediator effects will be computed and their statistical significance assessed. We propose to use multiple imputation [99, 100] and an analyses based on total ISI change over the course of the study. Additional mediator analyses will be performed for relevant measures listed in Table 5.

Likelihood of Obtaining Useful Results. For our primary hypothesis we considered a target power of 80% with a two-tailed test at 5% significance in an Intention-to-Treat (ITT) analysis. We will require 60 subjects per group (for a total of 120 in the two groups) to detect a main effect of treatment group with an effect size that increases R-squared by 6% or more, with respect to the continuous outcome variable (ISI improvement). Thus we feel that the sample of 60 per group is adequate. Power analyses were computed using G*Power Version 3.1.9.2 [101].

Considerations Regarding Sleep Medication Changes During the Study. Tentatively, we would consider patients who required a sleep medication increase a treatment failure and they would be scored accordingly. We would interpret a decrease in medications a sign that therapy was working and assume that the ISI ratings would reflect a treatment success. We plan to monitor these assumptions with our statistical team and adjust our analyses appropriately.

Other analyses. The above is meant to be a brief outline of our analytic approach. Other analyses will be conducted including examination of secondary outcomes such as Quality of Life measures.

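### The primary model adjusts for PTSD severity and SSRI use only if the arms are seen to differ, with no threshold; it should always adjust for their baseline values.

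*Combined protocol and SAP*

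**What the plan says.** Under Primary Hypothesis 1, the SAP regresses ISI change (6 weeks versus baseline) on treatment, with analogous models at 16 and 24 weeks. Treatment is the only term named without a condition. The covariate sentence reads: "We will covary for comorbid PTSD severity and amount of medication use (SSRIs) as required, if the frequency of such differs by treatment group".

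Under Secondary Hypothesis 2, the SAP returns to the same two factors: "Baseline Medication use and PTSD should be similar across groups due to randomization and use of the blocking procedures". The section it cites for the blocking is not in the supplied text. Section 2a of the protocol describes the allocation only in general terms ("Our hypotheses will be tested in a randomized parallel groups design") and names no blocking factors.

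A separate rule covers the exploratory moderator models: "The analysis may be adjusted for other covariates (age and alcohol use) if they are significantly different between groups at baseline despite randomization". The mediator models take over whatever results: "Each model will be adjusted for the same covariates described above".

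The sample-size paragraph (Likelihood of Obtaining Useful Results) plans 60 per arm for 80% power, two-sided 5%, to detect "an effect size that increases R-squared by 6% or more".

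**The concern.** Four features of the rule are open to objection.

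- **It leaves the model undecided.** There is no threshold, no test and no statement of who decides or when. Frequency is also not a workable criterion for a severity score or an amount of medication. Two statisticians could follow the text and fit different primary models.
- **It uses the wrong trigger.** A difference between arms does not show whether a factor predicts ISI change. A strongly prognostic factor that happens to be balanced is left out, and an irrelevant one that happens to be unbalanced is put in.
- **It works against the design.** If allocation was blocked on PTSD and medication use, an imbalance will rarely be seen, so the factors the design protects are the ones the model is least likely to contain.
- **It does not tie the covariates to baseline.** That word appears only in the later exploratory section.

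At stake are power for the primary comparison, a nominal 5% test that may run below 5%, and a model choice that cannot afterwards be shown to have been fixed in advance.

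**Working it through.** **Inputs from the SAP.** N = 120 (60 per arm), two-sided 5%, R-squared increase of 6%.

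**The plan's own figure.** With treatment as the only predictor:

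- f² = 0.06/0.94 = 0.0638, so d = 2√0.0638 = 0.505.
- λ = N·f² = 120 × 0.0638 = 7.66.
- The noncentral F test with 1 and 118 df gives power of 78.4%, within 2 points of the 80% target.

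**Assumed inputs.** The documents do not say how much ISI-change variance PTSD severity and SSRI use explain. I take R² = 5, 10 and 20%, shared equally between two binary factors. The trigger for adding a covariate is taken as a baseline difference at p<0.05 or p<0.20.

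**Closed-form check.**

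- *Always adjusting* divides the residual variance by 1/(1−R²), so λ = 7.66/(1−R²) = 8.06, 8.51 and 9.57. With 1 and 116 df, power is 80.4, 82.5 and 86.6%.
- *Stratified allocation, covariates left out.* The treatment estimate has variance reduced by the factor (1−R²), but the unadjusted model does not credit the reduction. Type I error is therefore about P(|Z| > 1.96/√(1−R²)). The cut-points are 2.011, 2.066 and 2.191, giving 4.4, 3.9 and 2.8%.

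**Simulation.** 40,000 trials per setting, with Monte Carlo SE about 0.1 point for type I error and 0.2 point for power. Each cell lists R² = 5/10/20%. Power is in percent.

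| Allocation (assumed) | Rule fires, p<0.05 / p<0.20 | Power, rule at p<0.05 | Power, rule at p<0.20 | Power, always adjust |
|---|---|---|---|---|
| A. Stratified blocks of 4, covariate is the blocking factor | 0% / 0% | 79.0/79.7/81.1 | same (never fires) | 80.5/82.6/86.9 |
| B. Stratified, half the covariate variance within strata | 1.2% / 14% | 78.3/78.4/79.4 | 78.4/78.8/80.0 | 79.7/81.8/86.3 |
| D. Unstratified | 11% / 33% | 78.8/78.3/78.9 | 79.0/78.9/80.4 | 80.1/81.5/85.9 |

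Type I error, rule at p<0.05 against always adjusting:

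- A: 4.5/3.9/3.0% against 5.1/5.1/5.2%.
- B: 4.7/4.5/3.8% against 4.9/5.1/4.9%.
- D: 4.9/4.7/4.5% against 4.9/5.1/5.0%.

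The mean unadjusted estimate lies within 0.003 of the truth throughout.

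**Gain from always adjusting** (last column minus each rule column):

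- R² 5%: 1.1 (D, p<0.20) to 1.5 points (A).
- R² 10%: 2.6 (D, p<0.20) to 3.4 points (B, p<0.05).
- R² 20%: 5.5 (D, p<0.20) to 7.0 points (D, p<0.05).

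A further setting, C, repeats B with 15% random loss. It is illustrative: the documents give no loss rate, although Section 9e item 6 does remove some participants after a serious adverse event ("However, data from such subjects will not be included in statistical analyses since such SAEs may affect sleep"). In it the gain at R² 20% with the 5% trigger is 79.7 − 71.7 = 8.0 points.

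**Weak covariates.** In an unstratified run with normal covariates (20,000 trials, SE about 0.3 point), always adjusting against the rule gave 78.4 against 78.7% at R² = 1%, and 79.1 against 78.6% at both 2% and 3%. At R² = 0, always adjusting costs at most 0.7 points of power against the unadjusted test, over all settings including C.

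**If the choice is not mechanical.** In a separate unstratified simulation (6,000 trials per setting), an analyst who took the smaller of the adjusted and unadjusted p-values would have type I error of 5.8 to 7.8% for R² from 5 to 30%. The plan does not propose this, but its wording does not exclude it.

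**The case against.** The best case against the point is that little is at risk. The estimate is unbiased, a mechanically applied rule does not inflate type I error, and inflation needs an analyst who picks by p-value, which the SAP does not plan. All of that stands, and it limits the point to lost power and an open model choice.

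The size of the power loss rests on an assumption. No section reports how well PTSD severity or SSRI use predicts ISI change, and the larger gains appear only at 20% explained variance. Below about 3% the two approaches cannot be told apart. That stands too. It does not favour the conditional rule, because always adjusting then costs almost nothing.

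The stratified settings use an assumed block size and assumed factor definitions, since the section on blocking is not supplied. This is why an unstratified setting is shown beside them, and the direction is the same in both.

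The 78.4% should not be read as a shortfall in its own right. The 6% is a rounded figure: an R-squared increase of 6.25% gives f² = 0.0625/0.9375 = 0.0667 and power of 80.1% at 120.

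Read with the later section, baseline values are the natural meaning, so the timing gap is one of wording. The age and alcohol rule is peripheral, because it governs only exploratory models. Lastly, naming the covariates is not enough if their coding stays open. That is right, and the fix below covers it.

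**Conclusion.** The concern holds. The primary model is conditional on an observed difference with no stated threshold, nothing elsewhere makes the adjustment unconditional, and the trigger has no bearing on whether adjustment helps.

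The consequence is moderate. Depending on an assumed 5, 10 or 20% of ISI-change variance explained, the rule gives up about 1, 3 or 6 to 7 points of power without loss to follow-up. If allocation was stratified on these same factors, it also runs the nominal 5% test at about 4.5, 3.9 or 3.0%. The result is neither biased nor invalid. Because a better rule is nearly free, the change should be made, although the trial does not depend on it.

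**What to change.** In Primary Hypothesis 1, delete the clause that makes adjustment depend on a difference between arms. State in its place that baseline PTSD severity and baseline SSRI use are covariates in the 6-week model and in the 16- and 24-week models, whatever the observed balance. Name the PTSD instrument and the coding of SSRI use (yes/no or amount). If the blocking used categorised versions of these factors, name those and include them. Keep the unadjusted model as a prespecified sensitivity analysis.

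Under Secondary Hypothesis 2, replace the significance-test rule for age and alcohol use with fixed inclusion or a prespecified sensitivity analysis. The mediator models then inherit a settled covariate list.

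Make the change before the arms are compared, since afterwards the choice cannot be shown to be prespecified.

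The cost is SAP wording and 2 to 4 of about 118 degrees of freedom, with no more participants or visits. A PTSD checklist is among the instruments attached in Section 16 ("PTSD_Checklist_DSM5"), and Section 8i has a medication list taken at screening. The supplied text does not say that the checklist is given at baseline, so the sponsor should confirm this.

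### The moderator analysis appears to read a bootstrap interval for the crossing point as the range where CBT-I and ABT-I do not differ; with a weak interaction this labels most participants wrongly

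*Combined protocol and SAP*

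**What the plan says.** The relevant text is in the Statistical Analysis Plan at the end of the combined document, under Secondary Hypothesis 2 (moderators).

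- Model: "regression models for change in ISI on treatment, the continuous moderator and the treatment by moderator interaction".
- Interval: "We will use percentile, bootstrap confidence intervals to determine the moderator value, if any, at which there is a change in the optimal choice" between treatments, explained as "the point of intersection at which one treatment first surpasses another".
- Second use: "The confidence intervals will also show the moderator values, if any, for which the difference between treatments is statistically or clinically insignificant".

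Between the last two, the SAP says that the results will guide the choice of treatment for individuals and estimate the advantage of one treatment at a given moderator value. It specifies no separate interval for that advantage. It does not require the interaction to be supported, and it has no rule for a crossing outside the observed range. The analyses are labelled exploratory.

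The sample size rests on the main effect alone (paragraph on the likelihood of obtaining useful results): "we considered a target power of 80% with a two-tailed test at 5% significance in an Intention-to-Treat (ITT) analysis", with "We will require 60 subjects per group (for a total of 120 in the two groups") to detect an "effect size that increases R-squared by 6% or more, with respect to the continuous outcome variable (ISI improvement").

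**The concern.** Write b1 for the treatment coefficient (at the moderator mean) and b3 for the interaction. The lines cross at −b1/b3, which is a ratio. When b3 is small relative to its standard error, its resampled values fall on both sides of zero and the resampled crossing points scatter to large negative and large positive values. The 2.5 to 97.5 percentile interval is still finite, and it usually spans the middle of the data.

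The region where the treatments do not differ significantly is a different object. It is the set of moderator values x at which the test of b1 + b3·x does not reject. With a real treatment effect and a weak interaction, that set is the outer parts of the moderator scale and excludes the centre.

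If the crossing-point interval is used for both purposes, the report could say that the treatments do not differ for nearly everyone, while the same model shows a significant difference for the average participant. Moderators are a stated secondary aim, meant to help personalise therapy, so readers would take that label seriously.

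**Working it through.** **Inputs from the SAP.** 60 per arm; two-sided 5%; target power 80%; R-squared increase of 0.06; moderator model as quoted.

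**Assumptions, since the documents give no figures.** Standard-normal moderator, residual SD 1, and a moderator slope of 0.3 where a slope is needed. Interaction sizes from 0 to 1.2 SD of outcome per SD of moderator.

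**1. The plan's own figure.** f² = 0.06/0.94 = 0.0638, so d = 2·√0.0638 = 0.505. The noncentral F test at N = 120 gives 78.4% power. The two-means formula gives 62 per arm, and N = 120 reaches 80% at R-squared 0.0623, which rounds to 6%. The stated size therefore reproduces to rounding.

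**2. Power for the interaction.** The standard error of b1 and of b3 is about 2/√120 = 0.183. Two-sided power for b3 = 0.1, 0.2, 0.3, 0.4 and 0.6 is about 8%, 19%, 38%, 59% and 91%. Unless moderation is strong, a non-significant interaction is the more likely result.

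**3. The correct non-significant region at the expected estimates.** The difference is non-significant where |b1 + b3·x| ≤ 1.96 × 0.183 × √(1 + x²). With b3 = 0 this becomes 0.505 ≤ 0.358·√(1 + x²), so |x| ≥ √((0.505/0.358)² − 1) ≈ 1.00.

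| b3 | Crossing (SD) | Non-significant region (SD) |
|---|---|---|
| 0 | none | outside (−1.00, 1.00) |
| 0.1 | −5.05 | outside (−0.70, 1.55) |
| 0.2 | −2.53 | outside (−0.51, 2.81) |
| 0.3 | −1.68 | outside (−0.40, 8.37) |
| 0.4 | −1.26 | inside (−12.3, −0.32) |
| 0.6 | −0.84 | inside (−2.38, −0.23) |

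The region is a single bounded interval only once |b3| exceeds 1.96 × 0.183 ≈ 0.36, that is, once the interaction is itself significant. In every row the moderator mean (x = 0) lies where the difference is significant.

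**4. What the percentile interval of −b1/b3 does.** Several independent simulations used d = 0.505 and 60 per arm, with up to 2,000 trials per scenario and up to 1,000 resamples per trial.

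Among trials with a significant difference at the moderator mean, the crossing-point interval contained the mean in:

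- about 94–95% with b3 = 0 (median interval width 58 to 60 SD);
- 72–75% with b3 = 0.25;
- 25–28% with b3 = 0.5;
- about 2–4% with b3 = 0.8.

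Among trials with a significant primary result (400 trials simulated per interaction size), the share of participants labelled as showing no difference was:

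| b3 | By crossing-point interval | By pointwise interval of the difference |
|---|---|---|
| 0 | 98% | 29% |
| 0.2 | 86% | 30% |
| 0.4 | 64% | 32% |
| 0.6 | 42% | 34% |
| 0.8 | 34% | 33% |
| 1.2 | 25% | 25% |

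The average share of the ±2 SD range that is both significant and inside the crossing-point interval depends on the yardstick. Against pointwise tests it is 47%, 37% and 13.5% at b3 = 0, 0.25 and 0.5. Against a Scheffé band it is about 30%, 24% and 9%.

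**5. Restricting to significant interactions.** Containment of the mean then falls to about 11% at b3 = 0.25 and 6–7% at b3 = 0.5.

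**The case against.** The strongest reply is that the paragraph was never meant this way. It says that intervals will help to find the crossing, which is not quite the same as putting an interval on it. It promises the advantage at a given moderator value, and it speaks of clinical insignificance. An interval in moderator units cannot show that a difference in ISI is clinically small; only an interval on the difference can. On that reading the plan is close to the remedy below. This stands as a possible reading, but the only interval that the paragraph ties to a named quantity is the one for the crossing, and the later sentence refers back to it.

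The SAP also allows that there may be no crossing. That is fair, but it gives no rule for deciding so, and a percentile interval returns finite limits regardless.

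The analysis is exploratory, the SAP calls itself a brief outline, and it cites a Table 5 and a numbered section that are not in the document. All this limits the stakes.

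Three stronger readings are tempting and are not supported:

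- A reader might infer that the interval is the exact reverse of the correct region. It is not: it takes in the middle and the near wings and drops only the far tails.
- A reader might infer that percentile intervals for a true crossing point have poor coverage. In simulation coverage was 94–97% at interactions of 0.1 to 0.5, against about 94–95% for Fieller sets. The fault lies in using the interval for a second purpose.
- A reader might infer that a simultaneous band is essential. Pointwise intervals do flag some value within ±2 SD in 14% of trials with no effect at all, but in an exploratory analysis the choice is a preference.

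**Conclusion.** The concern holds on the plain reading of the moderator paragraph. With a weak or unsupported interaction, the interval would label most participants as showing no difference even when the model finds a significant difference at the moderator mean. In simulation this happened at the mean in about 94% of such trials with no interaction, 72–75% at 0.25 SD per SD and 25–28% at 0.5. It nearly disappears at 0.8, and it is much reduced whenever the interaction is itself significant. These figures rest on the SAP's planning effect and on the assumed moderator distribution, residual SD and interaction sizes.

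A reader might go further and infer that the primary conclusion is at risk, or that the sponsor will certainly report contradictory results. The documents support neither. The primary test is a separate regression ("we will regress change in ISI on treatment (CBT-I versus ABT-I; 6 weeks vs. baseline") and is unaffected, and the wording leaves room for a sound reading. The point is a should-fix correction to an exploratory analysis.

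**What to change.** State in the SAP which quantity each interval is for.

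- Take the non-significant region from the confidence interval of the treatment difference b1 + b3·x over the observed moderator range (the Johnson-Neyman approach), not from the crossing-point interval. The interval may be bootstrap or model-based, and pointwise or, if preferred, simultaneous; say which.
- Report a crossing point only when the interaction is supported and the crossing lies inside the observed range. Alternatively, give a Fieller set and accept that it may be unbounded.

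The cost is a few sentences of SAP text and a few lines of code, with no new data. The small downside is that the report will often say that no crossing point can be located.
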